serve as the control site in which training will be provided via the virtual/remote training lead by a trained OT; 5 PACE organizations will serve as the comparison and be trained through the online training site. Prior to randomization, we will carefully examine PACE organizations on important variables such as size, location (urban; rural) percent of persons with dementia, and staff: participant ratio. In each site, one occupational therapist (OT) and one nurse (RN) will be trained (e.g., 5 OTs and 5 RNs in virtual/remote training sites; 5 OTs and 5 RNs in online training sites for a total of 10 OTs and 10 RNs or 20 health providers) Re-randomization procedures. Because COPE will be delivered by PACE staff to multiple participants with dementia within each organization, randomization at the individual participant level could lead to significant contamination between treatment and control conditions within an organization. Prior to randomization, we will collect organization-level data and have measures of organization size (or capacity), location (urban, suburban, rural), and summary characteristics of the participant population at each organization (e.g., percentage with dementia diagnosis, percentage minority). Because we will randomize ten organizations to five virtual/remote and five online training organizations, notable and problematic imbalances on at least a few organization-level characteristics could easily occur by chance in a single randomization. Methodological innovations are needed to achieve balance on these multiple organization-level characteristics while still maintaining the experimental rigor and inferential value of true random assignment. [name] will implement a re-randomization approach to achieve these important methodological goals. The balance match weighted (BMW) design is an innovative re-randomization procedure that is particularly well suited to our goals (54). Using the BMW approach, we will: 1) finalize the list of important covariates for which we desire matching or balancing across intervention and control organizations, 2) generate 20 lists of random assignments for these 10 organizations into intervention and control conditions, 3) calculate propensity scores of intervention assignment as a function of the covariates, and 4) select the random assignment list that minimizes the propensity score differences between intervention and control organizations. The BMW approach provides a random assignment distribution that has an optimal balance on multiple organization-level characteristics. This will result in even greater control over potential covariate influences and provide somewhat greater power to detect a COPE program effect. Treatment Conditions: COPE Online Training: Trinity PACE Organizations assigned to the COPE Online Training will receive the 10- Module training program described above. Designated OT/ RNs at the assigned PACE Organization will be emailed unique log-in details and instructions for completing the online training within the 3-day training window (to align with control group training) but at their own pace. Log-in details including date, time and duration in training sessions will be tracked. COPE Virtual/Remote Training: We will train one OT and one RN at each of the five PACE organizations randomly assigned to the virtual/remote training. [name] will conduct trainings. Our training program will involve up to 3 days which include about 4 hours of initial readings, PowerPoint presentations, and case presentations. Training will take place via web conference (via GoToMeeting.com or other platform) sessions. We will offer three of these training sessions to accommodate COPE staff members' schedules and assure an interactive process. Further, interventionists will participate initially in monthly tele-conference or web conference sessions and then 6 times a year over the duration of intervention delivery. Sessions will involve case presentations, troubleshooting, and adherence monitoring. We have used this approach in multi-organization endeavors with up to 15 interventionists actively participating by telephone. Using a structured agenda and assigning case presentations a priori facilitates productive discussions. We have allocated funds for COPE staff members time to participate in training and follow-up bimonthly calls to troubleshoot cases. Both groups will participate in monthly debriefing sessions which will be recorded and used to understand type of questions asked, problems encountered etc., to compare the two training groups. We have a specific agenda and methodology for interventionists to provide case reports (55). We will also establish a password secure and encrypted email list serve for interventionists to post challenges and receive feedback from PIs and other interventionists.

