
**PHASE 3 (Aim 3): Efficacy of COPE on PACE participant outcomes by type of COPE training.**  
This aim will be accomplished by evaluating dyad outcomes of the COPE program under the two different training approaches. Following training, each of the PACE organizations will enroll 5 persons with dementia and their caregivers in the study. This will yield 50 family dyads (25 dyads in traditional training sites and 25 dyads in online training sites). At 4 months, all dyad study outcomes will be assessed

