**Analysis of Aim 3:** To compare the efficacy of COPE on participant outcomes. One-sided to-sample t-tests will be used to examine non-inferiority at 4-months. Upper and lower 95% confidence intervals will be presented for means and medians. Assumptions of normality and equality of variance between groups will be evaluated using Shapiro-Wilk and modified Levene's tests, respectively. Should the variances be unequal, the Aspin-Welch unequal variance t-test will be used to examine non-inferiority; should the normality assumption be violated, the non-parametric Mann-Whitney U test will be used to examine non-inferiority. Descriptive statistics including measures of central tendency (mean, median, mode) and variation (standard deviation, interquartile range, range) for continuous measures as well as frequencies and percentages for dichotomous and categorical variables will be run for all measures at each timepoint. Outliers will be assessed by visual inspection of distributions and checked for accuracy. Histograms and Q-Q plots will be used to evaluate assumptions visually. Two-sample t-tests (or non-parametric Wilcoxon tests, as necessary) and Fisher's exact tests will be used to examine differences in demographic and treatment variables between intervention groups at each timepoint. To demonstrate that the online COPE training intervention is the same or better than the virtual/remote training intervention with regards to participant outcomes, one-sided two-sample t-tests will be used to examine non-inferiority at 4 months. Upper and lower 95% confidence intervals will be presented for means and medians. Assumptions of normality and equality of variance between groups will be evaluated using Shapiro-Wilk and modified Levene's tests, respectively. Should the variances be unequal, the Aspin-Welch unequal variance t-test will be used to examine non-inferiority; should the normality assumption be violated, the non-parametric Mann-Whitney U test will be used to examine non-inferiority.

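### The power gain promised from best-of-20 re-randomization is not assured, because the specified tests ignore the organization, the balancing covariates and the baseline outcome

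*Combined protocol and SAP*

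**What the plan says.** **Design.** Under Study Procedures, Phase 2 (and in near-identical words under Research Plan, Phase 2), the plan states that "we will randomize ten organizations to five virtual/remote and five online training organizations". The team will "generate 20 lists of random assignments for these 10 organizations into intervention and control conditions" and then "select the random assignment list that minimizes the propensity score differences between intervention and control organizations". The candidate covariates are "organization size (or capacity), location (urban, suburban, rural), and summary characteristics of the participant population at each organization"; the final list is still to be settled. The stated benefit is that this will "provide somewhat greater power to detect a COPE program effect". No calculation or figure accompanies that sentence.

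**Sample.** For Aim 3, "each of the PACE organizations will enroll 5 persons with dementia and their caregivers in the study", which makes 25 dyads per arm and 50 in all. For Aim 1 there are 20 staff, two per organization.

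**Analysis.** For Aim 3, "one-sided two-sample t-tests will be used to examine non-inferiority at 4 months", with the Aspin-Welch or Mann-Whitney test as fallback. Aim 1 names an independent-samples t-test and Fisher's exact test. Aim 2 names a kappa for automated against human ratings, but no test between arms. In the text available, no analysis contains an organization term, a balancing covariate, a baseline value, a propensity weight or a re-randomization test. The unit of analysis is not stated; the sample description points to the individual dyad or staff member.

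**Baseline data.** Study Instruments has the caregiver instruments given at baseline and at four months. The Aim 1 analysis has surveys before and after training.

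**The concern.** Two features of the design should reach the analysis and do not.

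First, organizations are randomized and people within them are measured. A test that treats 50 dyads as independent leaves the variation between organizations out of its standard error. In a non-inferiority trial, an error bar that is too narrow makes it too easy to declare the online training acceptable.

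Second, choosing a well-balanced list makes the difference between arms less variable, but an unadjusted test does not see this. Its standard error still contains the variation that the balancing removed. The plan takes credit for a precision gain that its analysis is not built to use.

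The sentence also misnames the target. Risk / Benefit Assessment says that all families receive COPE, so the trial cannot estimate an effect of COPE, only a difference between two ways of training its providers.

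**Working it through.** The plan gives no power figure to reproduce, so the check asks what the specified tests do under this design.

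**Inputs from the documents:** 10 organizations, 5 per arm; best of 20 lists; m = 5 dyads per organization (n = 25 per arm), or m = 2 staff (n = 10 per arm).

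**Assumed, because the documents give none:** one-sided level 2.5% (matching the 95% intervals); ICC ρ from 0.05 to 0.20; share R² of between-site variance explained by the balancing covariates, from 0 to 1; four covariates; normal outcomes with total SD 1.

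**Step 1: what the selection does.** In simulation, with balance measured by Mahalanobis distance, best of 20 cuts the variance of covariate imbalance to f = 0.23 of a single draw with four covariates (0.40 with six). Selecting on logistic propensity scores gave the same reduction. The between-site variance that still reaches the arm difference is multiplied by g = 1 − R²(1 − f).

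**Step 2: actual against reported variance, individual-level t-test.**
- Actual: V = (2/n)[(1 − ρ) + mρg]
- Reported on average: U = (2/n)[(1 − ρ) + (4m/(n − 1)) ρ(9 − g)/8]
- Type I error ≈ P(t > t_crit/√(V/U)) on 2n − 2 degrees of freedom

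Example with 50 dyads, ρ = 0.10, R² = 0.5:
- g = 1 − 0.5 × 0.77 = 0.615
- V bracket: 0.90 + 5 × 0.10 × 0.615 = 1.2075
- U bracket: 0.90 + 0.8333 × 0.10 × 8.385/8 = 0.9873
- Ratio 1.223, root 1.106, so the true standard error is about 11% larger than the reported one
- 2.011/1.106 = 1.818 on 48 df, giving a type I error of 3.8%

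| ICC | R² = 0 | R² = 0.5 | R² = 1 |
|---|---|---|---|
| 0.05 | 3.7% | 3.1% | 2.6% |
| 0.10 | 4.9% | 3.8% | 2.6% |
| 0.20 | 7.4% | 5.1% | 2.8% |

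Simulation with 20,000 runs per cell agrees: 3.2% and 3.8% at R² = 0.5 for ICC 0.05 and 0.10; 7.5%, 5.0% and 2.8% across the ICC 0.20 row.

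For the 20 staff the formula gives 2.7% (ICC 0.10) and 2.8% (ICC 0.20) at R² = 0.5. It falls clearly below nominal only at large ICC with R² of about 0.8 or more (2.0% at ICC 0.20, R² = 1).

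**Step 3: the same comparison for a t-test on the 10 site means (8 df).**
- V = 0.4[ρg + (1 − ρ)/5] and U = 0.4[ρ(9 − g)/8 + (1 − ρ)/5]
- At ρ = 0.20, R² = 0.5: 0.2830/0.3696 = 0.766; 2.306/0.875 = 2.635, giving 1.5%
- At ρ = 0.05, R² = 0.5: 2.1%

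This test is conservative, and markedly so only when the covariates are clearly prognostic.

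**Step 4: power of the unadjusted tests, single draw to best of 20 (simulated).** Effects are distances from the margin, in SD.

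| Setting | 0.4 SD | 0.8 SD | 1.2 SD |
|---|---|---|---|
| Dyads, ICC 0.10, R² 0.5 | 0.317 → 0.304 | 0.759 → 0.777 | 0.969 → 0.978 |
| Dyads, ICC 0.20, R² 1 (limit) | 0.345 → 0.290 | 0.741 → 0.794 | 0.952 → 0.984 |
| Site means, ICC 0.20, R² 0.5 | not shown | 0.454 → 0.440 | 0.792 → 0.803 |

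A less variable estimate set against an unchanged standard error helps when power exceeds about one half and hurts below that. Part of the loss at dyad level is simply a smaller excess of false positives.

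**Step 5: analyses that use the design.** Organization level, best of 20, one-sided 2.5%, 0.8 SD, R² 0.5:

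| Analysis | ICC 0.05 | ICC 0.10 | ICC 0.20 |
|---|---|---|---|
| Unadjusted | 0.62 | 0.56 | 0.44 |
| All four covariates (4 df) | 0.49 | 0.48 | 0.44 |
| One ideal prognostic index (7 df) | 0.62 | 0.60 | 0.56 |

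With the organization's baseline mean as the single adjuster at ICC 0.10, power goes from about 0.56 to 0.62 (baseline correlation 0.5) or 0.77 (correlation 0.7). If the baseline is unrelated to the outcome, it loses about 6 to 7 points. Type I error stays near nominal or slightly below.

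**The case against.** The strongest defence is that the sentence promises only a modest gain and is literally true where trials are usually planned. At 80 to 90% power, the unadjusted tests do gain a little from the balancing. This stands: the plan cannot be faulted for claiming a property that never exists. What remains is that the gain depends on effect size, ICC and covariate strength, none of which the plan states, and that it turns slightly negative where power is low.

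A second defence is that covariate adjustment with ten clusters is debatable. This stands too. Adjusting for the whole list costs power at low ICC (0.49 against 0.62 at ICC 0.05). It is an argument for a single adjuster, not for ignoring the organization.

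A reader might go further and infer that re-randomization followed by unadjusted tests gives a type I error well below nominal and no power gain at all. The documents do not support that. It describes a test on ten site means with prognostic covariates at one moderate effect size, and no section specifies a site-mean test. For the tests as they most naturally read, unmodelled clustering pushes the Aim 3 error rate the other way.

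**Conclusion.** The concern holds in a limited form. The power gain is asserted without support, and the specified tests do not reflect how the trial was randomized. For the 50-dyad test, the more likely fault is error bars that are too narrow. The inflation nearly disappears only if the balancing covariates explain almost all variation between sites. Aim 1 is much less affected, with two staff per organization.

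The size of each figure rests on the assumed ICC, R², level, effect size, baseline correlation and number of covariates. The direction for Aim 3 needs only some clustering that the covariates do not fully explain. That no COPE effect can be estimated rests on no assumption.

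**What to change.** 1. State the unit of analysis. Analyse Aims 1 to 3 on organization-level summaries, or in a cluster model with a small-sample correction.
2. Adjust for the baseline value of the same outcome where it is collected (caregiver instruments, pre-training survey). Where there is none, as for fidelity, adjust for at most one balancing covariate named before unblinding, not the whole list.
3. Make the power sentence conditional on that adjustment, in both places where it appears, and refer to a difference between training modes instead of a COPE program effect.

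An exact re-randomization test alone is not a good substitute. The 252 possible lists form 126 mirror pairs, and the best list is kept with probability [1 − (125/126)^20]/2 = 0.074, as is its mirror image. If that list is the one used, no one-sided p-value can fall below 7.4%. In simulation, at a one-sided 5% level and 0.8 SD, such a test had power of only 0.33 to 0.39.

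The cost is SAP wording, one degree of freedom, and roughly 3 to 7 points of power if the adjuster proves not to be prognostic. Moving to organization level also shows lower power than the dyad-level test appears to have (about 0.56 against 0.78 at ICC 0.10 and 0.8 SD, unadjusted). Part of that difference is the false-positive excess being removed.

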5. Partnering with Trinity PACE, the largest PACE provider in the US, will provide robust, generalizable data. The development of this proposal reflects extensive collaboration among study team members and Trinity Health. Trinity Health PACE is a member of Trinity Health, one of the largest multi-institutional Catholic health care delivery systems in the US. Trinity Health PACE is one of the leading providers of PACE in the country based on the number of available programs. In preparation for this application, during meetings with Trinity Health and Trinity PACE leadership, leaders, administrators and staff all demonstrated clear engagement, and expressed keen interest in improving dementia care practices, and a readiness and capacity for change. In preparation for this RFA 10 Trinity Health PACE organizations expressed willingness to participate (see Letter of Support). PACE Organizations for participation in this trial fit these criteria: a) have a minimum of 90 enrolled participants; b) have OT and RN staff; and c) express willingness to participate and accept random assignment. The lessons learned in this study concerning training and fidelity methodologies will enable us to move rapidly forward with a large, multi-site pragmatic trial to test embedding COPE within existing Trinity PACE. As Trinity PACE Organizations will be highly generalizable to all PACE programs nationally as they all have similar financial and clinical

structures regardless of their management organization nationally.

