
**PHASE 2** - Evaluation of Online Training Program in Interventionist Uptake and Fidelity Phase 2 of this study involves a series of activities designed to evaluate whether an online training program is the same or better in improving interventionist uptake of- and fidelity to- COPE principles and protocols compared to the virtual/remote training lead by a trained OT. Eligibility and enrollment: Ten participating Trinity PACE Organizations will participate via webinar in a brief orientation/training to the study and project logistics. Next, Trinity Health PACE organizations will be randomized into two groups using the re-randomization procedures described in the paragraph below; 5 PACE organizations will

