**Consent Process:** All informed consent guidelines of the University of Pennsylvania Institutional Review Board (IRB) will be followed. We will use a multi-stepped approach to gaining consent from Trinity Health PACE occupational therapists and nurses (OT/RNs) using email, DocuSign, PennBox, or mail to obtain consent signatures. The Penn site will obtain consent from OT/RNs who agree to complete the training program. Discussions about consent will take place between the study team and OT/RN participants via phone and video conferencing programs (Skype, FaceTime, Blue Jeans, Zoom, etc.). Two Trinity Health PACE sites will participate in a pilot test of all study procedures. OTs and RNs from these sites will sign the "OT and RN ICF Pilot Test" document. This version of the ICF notes that these participants will participate in the pilot test or beta test. Then, recruitment of caregivers will be done by Trinity research liaisons who will read a Penn-approved recruitment script to caregivers or share flyers with study team contact information to use. Interested caregivers will contact study team members (if received flyer) or be contacted via telephone by Penn study team members (if consented to have their contact shared) who will provide more detail about the study, answer questions, and read the caregiver verbal consent script. Within the script is language that informs the caregiver that 1) the

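### The plan does not say when, by whom or by what rule the OT and RN trainees are named and consented relative to disclosure of the site's assignment, so choice of staff to suit the training format cannot be excluded

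*Combined protocol and SAP*

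**What the plan says.** The Specific Aims place the Aim 1 outcomes (confidence, competency, satisfaction) on the OTs and RNs. The unit of randomization is the organization. In Study Procedures, Phase 2, the ten organizations first attend an orientation webinar. Then: "Next, Trinity Health PACE organizations will be randomized into two groups using the re-randomization procedures". The split is five and five: "Because we will randomize ten organizations to five virtual/remote and five online training organizations". The quota is the same in both arms: "In each site, one occupational therapist (OT) and one nurse (RN) will be trained". The Phase 2 text of the Research Plan has the same structure.

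Individual trainees enter the account under Treatment Conditions. For the online arm: "Designated OT/ RNs at the assigned PACE Organization will be emailed unique log-in details and instructions for completing the online training". For the comparator: "We will train one OT and one RN at each of the five PACE organizations randomly assigned to the virtual/remote training".

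The entry criteria for organizations (Innovation, item 5) ask for at least 90 enrolled participants and that the site "have OT and RN staff; and c) express willingness to participate and accept random assignment". Naming the two trainees in advance is not a criterion. The Consent Process section says "The Penn site will obtain consent from OT/RNs who agree to complete the training program" and gives no timing relative to randomization.

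The re-randomization step lists organization-level covariates only: size or capacity, location, and summary features of the participant population. The Analysis Plan for Aim 1 names an independent-samples t-test, a chi-square-type test and Fisher's exact test, with no adjustment. Study Instruments provides for a pre-training survey and for trainee demographics, including education and years employed.

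**The concern.** Randomizing organizations balances, in expectation, the staff available at each site. It does not protect the choice of which OT and which RN take part if that choice is made by someone who knows the format. The formats differ visibly: self-paced modules done alone, against live web-conference sessions with case presentations. Trainees cannot be blinded to their own format, so naming staff before disclosure is the main design safeguard, and the plan does not contain it.

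The same 20 people deliver the sessions rated in Aim 2 and treat the 50 dyads in Aim 3, so a difference in who was chosen would run through all three aims. In a non-inferiority comparison, a shift favouring online makes a false conclusion of same-or-better more likely. A shift favouring the comparator could hide a sound online programme.

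**Working it through.** **Count.** 10 organizations × (1 OT + 1 RN) = 20 trainees, 10 per arm, as the protocol states. It gives no margin, alpha, SD or power for Aim 1, so there is no sample-size figure to reproduce.

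**Timing, point by point.**
- Randomization: placed directly after the webinar. No naming or consent of staff is mentioned before it.
- Online arm: the sentence dates the sending of log-ins, which must follow assignment in any design. It does not date the designation.
- Comparator arm: the sentence dates the training, not the choice of trainee.
- Consent: no timing relative to assignment.
- Organization entry: acceptance of random assignment by the site, nothing about named staff.

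The order of the text fits designation after assignment but does not establish it.

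**Do other features close the gap?**
- Balancing uses no trainee characteristic.
- The Aim 1 tests use no baseline covariate.
- The pre-training survey and demographics would reveal some imbalance in knowledge, education or tenure, but no analysis uses them to correct it. A trait such as aptitude for self-directed learning is not among the listed measures.

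**Illustration of size.** Everything here except 10 per arm is an assumption: independent trainees (no clustering by site), outcome in SD units, online truly at the margin, and a selection shift *d* towards online.

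SE of the difference = √(1/10 + 1/10) = 0.447 SD. By the normal approximation at one-sided 5%, false non-inferiority = 1 − Φ(1.645 − *d*/0.447):
- *d* = 0.2: 1 − Φ(1.645 − 0.447) = 1 − Φ(1.198) = 11.6%
- *d* = 0.3: 1 − Φ(1.645 − 0.671) = 1 − Φ(0.974) = 16.5%
- *d* = 0.5: 1 − Φ(1.645 − 1.118) = 1 − Φ(0.527) = 29.9%

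The exact calculation uses the noncentral t with 18 df and noncentrality *d*/0.447:

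| *d* (SD) | one-sided 5% | one-sided 2.5% |
|---|---|---|
| 0 | 5.0% | 2.5% |
| 0.2 | 11.2% | 6.2% |
| 0.3 | 15.9% | 9.3% |
| 0.5 | 28.5% | 18.4% |

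A shift of the same size towards the comparator works the other way. At one-sided 5%, *d* = −0.2 gives 1.9%.

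**What shift is plausible?** The mean of the better of two standard normal draws is 1/√π = 0.56. If a site picks the better of two candidates on a trait correlated 0.2 to 0.5 with the outcome, the shift is 0.56 × 0.2 = 0.11 to 0.56 × 0.5 = 0.28 SD. With one candidate it is zero. A shift of 0.5 SD is therefore an upper illustration.

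**The case against.** A reader might infer that trainees are in fact designated and consented after assignment, knowing their format, and that the protection of randomization is lost. The documents do not support this. The word for designated staff fits people named earlier, for instance around the pre-randomization webinar, and the consent text is silent on timing. Organizations stay randomized, must "express willingness to participate and accept random assignment", and send the same quota in both arms.

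Scope for choice is also unknown. The documents give no number of OTs or RNs per site, and a site with one of each cannot choose. The contrast between formats is moderated: under Study Procedures both arms train remotely, the online window of 3 days is set to match the comparator, and three live sessions are offered to fit staff schedules. Pre-training knowledge and tenure are recorded, so some imbalance would be visible. The calculation rests on an assumed shift, alpha and direction.

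All of this stands as a limit on what can be claimed. It does not close the gap: no section requires naming or consent before disclosure, and no planned analysis would correct an imbalance once seen.

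**Conclusion.** The concern holds as a gap in the design as written. The sequence permits format-aware choice of the 20 people on whom Aim 1 is measured and on whom Aims 2 and 3 depend, and neither the organization-level balancing nor the unadjusted tests deal with it. It is not evidence that such choice occurs.

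Any bias could go in either direction and is zero at a site with no choice of staff. Under the stated assumptions, a shift of 0.2 to 0.5 SD towards online takes false non-inferiority from 5% to about 11-30% across the two methods of calculation. The lower part of that range is the more plausible. The change is worth making because it is cheap, not because the bias has been shown to be large.

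**What to change.** In the organization entry criteria (Innovation, item 5) and the Phase 2 enrollment text of both the Research Plan and Study Procedures, require the following before assignment is disclosed. Each organization names its OT and RN. Those two people consent to either training format and complete the pre-training survey and demographics. Any later substitution is reported by arm. Ranked reserves for each role are an option, not a necessity.

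Consent, survey and demographics are already planned, so this is mainly a reordering; the substitution report is a small addition. The price is that allocation waits for the last organization.

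Reordering may no longer be possible: the Consent Process section refers to staff consent forms signed before September 16th, 2022. If assignment has been disclosed, the protocol should state when and by whom trainees were named and consented, and whether the format was then known. The report should give trainee baseline characteristics and substitutions by arm. The Aim 1 knowledge comparison should be adjusted for the pre-training score, accounting for site. Adjustment covers only what was measured, so it is a partial remedy.
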